 Contact/Investigator:
 Phone Number:

If documentation of assurances has not been sent to the Office of Research, please explain:

A7. Research Category:

Cancer Related, Cancer - Adult

A8. Therapeutic Intent

Does this trial have therapeutic intent?

No

Section B: Exempt Request

B. Exempt From IRB Review

Not Applicable

Section C: Background Information

In the United States, almost 15 thousand people die from esophageal adenocarcinoma (EAC) every year. (Ries LAG, 2005). Barrett's Esophagus (BE) is a known precursor lesion that increases the risk of progression to EAC by 40 to 125 times. Despite this increased risk, specific biomarkers or imaging modalities to diagnose BE-associated dysplasia or neoplasia have yet to be completely developed. Therefore, currently, routine endoscopies remain the standard of care to detect early adenocarcinoma and dysplasia in BE patients. However, the sensitivity of standard white-light endoscopy with mucosal biopsy in diagnosing EAC in BE patients is less than 50% (Sharma). One of the reasons early EAC or BE-dysplasia is not picked up by standard endoscopy is that BE mucosa with dysplasia or early cancer is not endoscopically distinguishable from non-cancerous BE mucosa. Therefore, multiple biopsies (4-quadrant biopsies every 1-2 cm of BE

segments) are required to ensure that dysplasia or neoplasia is not missed. However, these extensive biopsy protocols lead to long procedure times and high costs while still missing dysplastic or neoplastic lesions. Moreover, the decision to perform an endoscopic mucosal resection cannot necessarily be determined until the histopathology is confirmed and a second endoscopy is performed. Our group, in collaboration with Rice University, has developed a low-cost (< \$3,500), portable, battery-powered, high resolution microendoscope (HRME) that can be inserted through the biopsy channel of any standard endoscope. When used with 1-5 ml of topical proflavine hemisulfate 0.01%, a fluorescent contrast agent, the device provides subcellular images of esophageal epithelium and can delineate the cellular and morphologic changes associated with neoplastic progression of BE to low-grade neoplasia, high-grade neoplasia and finally to esophageal adenocarcinoma. Topical proflavine has been used in confocal imaging in Europe and Asia with no adverse events to date and is being used under an IND issued by the FDA (#102,217).

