Preliminary ex-vivo data has been published in *Gastrointestinal Endoscopy*. This data confirmed that HRME images of Barrett's metaplasia and neoplasia could be correlated to gold standard histopathology. Moreover, our group recently conducted a small pilot study of HRME in a high risk BE population that demonstrated a sensitivity of 81% and a specificity of 85%. Most encouraging, however, was the negative predictive value of 95% that we achieved in this study. This suggests that areas that are deemed "non-neoplastic" on HRME may not need to be biopsied.

We believe that the next step in determining whether HRME can enhance the efficiency and yield of current surveillance is to perform a randomized, controlled trial comparing HRME to standard white light endoscopic protocol. Moreover, the in-vivo data we hope to collect will show that HRME will allow endoscopists to make informed real-time decisions regarding biopsies and endoscopic mucosal resections. Ultimately, we believe HRME can reduce the number of biopsies necessary as well as the total procedure time required to screen for BE-associated dysplasia and EAC. Therefore, HRME could reduce the overall cost of screening and become a much more attractive option for low-income communities.

As incidence rates for cancer rise, it is imperative that we improve early detection strategies. More importantly, it is critical that we develop cost-effective, robust platforms that can be used in community based screening/surveillance programs. We believe that successful results can be translated to other organ systems and, thus, help address the global costs of rising cancer incidence.

Section D: Purpose and Objectives

Our central hypothesis is that the low-cost HRME will increase the efficiency and yield of the current standard of endoscopic surveillance of BE. We believe the HRME will provide an in-vivo "optical biopsy" that will be comparable to gold standard histopathology and allow the endoscopist to make a more informed decision about whether to obtain a biopsy or even perform endoscopic therapy (i.e. endoscopic mucosal resection, EMR). Specific aims of this project are, in patients with known BE:

- 1a) to compare the diagnostic yield (defined as the proportion of mucosal biopsy samples with neoplasia) of HRME with directed biopsy to standard white-light endoscopy with 4-quadrant random biopsy (WL) for the diagnosis of BE-associated neoplasia in flat mucosa as well as mucosal lesions;

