The patient will be assigned to one of two groups: Group A: high resolution white-light endoscopy followed by random biopsy (WL) or Group B: high resolution white-light endoscopy plus HRME followed by directed mucosal biopsy (HRME). Randomization assignments (WL vs. HRME) will be computer-generated with allocation concealment using sealed envelopes.

Inclusion Criteria:

All consecutive outpatients with > 1 cm biopsy-proven Barrett's Esophagus who are undergoing standard of care endoscopic surveillance for metaplasia, dysplasia, or neoplasia.

Exclusion Criteria:

- Allergy or prior reaction to the fluorescent contrast agent proflavine
- Patients who are unable to give informed consent
- Known advanced adenocarcinoma of the distal esophagus, or dysplastic/suspected malignant esophageal lesion greater than 2 cm in size not amenable to EMR
- Patients with a history of a severe allergic reaction (anaphylaxis)
- Patients unable to undergo routine endoscopy with biopsy
- Women who are pregnant or breastfeeding
- Prothrombin time greater than 50% of control; PTT greater than 50 sec, or INR greater than 2.0
- Inability to tolerate sedated upper endoscopy due to cardiopulmonary instability or other
- Patients with known, untreated esophageal strictures, prior partial esophageal resection, or altered anatomy preventing passage of the endomicroscope
- Patients with known severe esophagitis
- Patients with suspected but no biopsy confirmed BE

F2. Procedure

Written informed consent will be obtained prior to study participation using the IRB-approved consent form. Identifying information collected includes D.O.B., age, gender, race and date of encounter. The patient will be assigned to one of two groups: Group A: high resolution white-light endoscopy followed by random biopsy (WL) or Group B: high resolution white-light endoscopy plus HRME followed by directed mucosal biopsy (HRME). Randomization assignments (WL vs. HRME) will be computer-generated with allocation concealment using sealed envelopes.

White Light Endoscopy (WL) Procedure (Group A)

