Patients assigned to the WL group will undergo careful standard examination of the upper GI tract with a standard high resolution endoscope (Olympus Corporation) without HRME. Endoscopic landmarks and BE characteristics will be described as listed in the previous section. Any mucosal lesions in the BE will be classified using the Paris classification. The endoscopist will predict whether BE and dysplasia are present based upon the white light endoscopic findings (endoscopic diagnosis) and whether neoplasia is suspected if there are any endoscopic lesions (endoscopic plan).

Mucosal biopsies of any discrete lesions will be obtained and placed in separate pathology containers per standard of care. Then, four-quadrant mucosal biopsies of the flat BE mucosa (a biopsy from each quadrant of the BE at each level) will be taken per standard of care: every 1 cm (for patients with suspected neoplasia) or every 2 cm (for patients undergoing routine surveillance), starting at the GE junction, moving proximally to the squamocolumnar junction. These mucosal biopsies will be obtained in a similar fashion to the standard Seattle biopsy protocol⁴. This biopsy protocol is commonly used for obtaining surveillance biopsies to sample representative areas of the entire length of the BE. Each level of the biopsies designated by the distance (in centimeters) on the endoscope from the patient's gums.

The total time of the procedure, as well as the time needed to complete the standard endoscopy and the time needed to take tissue biopsies, will be recorded. The co-investigator or research coordinator will indicate the biopsy number and location of the biopsy on a standardized BE map. The biopsies from each site will be placed in formalin and labeled according to the biopsy location.

Post-procedure, the endoscopist will inspect the map created by the coordinator and approve the data recorded. The number of biopsies obtained and biopsy specimen bottles sent for processing will be tracked to allow calculation of pathology costs.

High Resolution Microendoscopy (HRME) Procedure (Group B)

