Following the targeted biopsies, random four-quadrant biopsies of the flat BE mucosa will be taken with every 1 cm (for patients with suspected high grade dysplasia (HGD)) or every 2 cm (for patients undergoing routine surveillance), starting at the GE junction, moving proximally to the Z line per standard of care. Prior to the standard tissue biopsy, an HRME read will be obtained from the area (neoplastic vs. non-neoplastic). A superficial dimple will be made with the HRME of each imaged site to "mark" the imaged area for biopsy. The latter is commonly performed in imaging correlation studies and has not been shown to affect pathology.

Pathology

The fixed biopsies will be oriented/embedded in paraffin and sectioned to facilitate comparison between histology and HRME images. Afterwards the serial sections will be routinely stained with hematoxylin and eosin for histopathologic examination.

The biopsies or resected specimens (from EMR) obtained from the examined areas will be routinely processed and interpreted by a single expert gastrointestinal pathologist in a blinded fashion and graded according to the Vienna Classification. The pathologist will provide a diagnosis for each biopsy specimen in the cassette to allow correlation with the endoscopic and HRME findings. The histopathologic diagnosis for each biopsy will be recorded on a standardized data collection form.

Section G: Sample Size/Data Analysis

G1. Sample Size

How many subjects (or specimens, or charts) will be used in this study?

Local: 47 Worldwide: 100

Please indicate why you chose the sample size proposed:

Approximately 100 subjects with 50 in the WL-arm and 50 in the HRME-arm. We anticipate that 15-20% of subjects may be not complete their endoscopy for various reasons (lack of biopsies, loss of Barrett's mucosa, visualization of a lesion > 2 cm, inability to complete endoscopy, etc.) which would allow 40 in each arm. Since each patient only requires one visit for enrollment into the study, we expect that 80 patients will be enrolled and randomized and complete the study.

G2. Data Analysis

Provide a description of your plan for data analysis. State the types of comparisons you plan (e.g. comparison of means, comparison of proportions, regressions, analysis of variance). Which is the PRIMARY comparison/analysis? How will the analyses proposed relate to the primary purposes of your study?

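### The trigger for 1 cm rather than 2 cm four-quadrant biopsies is worded differently in the two arms, so biopsy density can differ for a reason unrelated to HRME

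*Protocol*

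**What the plan says.** Both arms take four-quadrant biopsies of flat Barrett's mucosa, starting at the gastroesophageal junction and moving proximally. Both give the 2 cm interval to routine surveillance, and both refer to standard of care. They differ in what moves a patient to 1 cm:

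- Group A (Protocol F2, White Light Endoscopy Procedure): "every 1 cm (for patients with suspected neoplasia) or every 2 cm (for patients undergoing routine surveillance".
- Group B (Protocol F2, High Resolution Microendoscopy Procedure): "every 1 cm (for patients with suspected high grade dysplasia (HGD)) or every 2 cm (for patients undergoing routine surveillance".

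In Group A the endoscopist is to "predict whether BE and dysplasia are present based upon the white light endoscopic findings", and also notes whether neoplasia is suspected where there are lesions. In Group B a neoplastic or non-neoplastic call and a plan are recorded for visible lesions before HRME imaging starts. Neither record is linked to the biopsy interval. The SAP does not mention the interval. The risk strata in G2 are not defined and are not linked to it either.

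**The concern.** In a randomised comparison, the rule that sets how many random biopsies a patient receives should be the same in both arms unless the difference is the intervention. Here the difference lies in the wording of a trigger and has nothing to do with HRME.

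The exposed outcomes matter to the trial. Aim 1b concerns the number of biopsies per procedure, and aim 3 compares procedure time, including biopsy acquisition. Section C states that "we believe HRME can reduce the number of biopsies necessary as well as the total procedure time required". Costs are involved too: "The number of biopsies obtained and biopsy specimen bottles sent for processing will be tracked to allow calculation of pathology costs". Biopsy count is also the denominator of the primary outcome, diagnostic yield. A difference between arms in any of these could come partly from the trigger.

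Stratifying by risk group need not remove this. If all average-risk patients are under routine surveillance, the arms agree in that stratum and any difference sits wholly in the high-risk stratum.

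**Working it through.** **The plan's own figure.** The only checkable figure nearby is the 40 completers per arm in G1: 50 × (1 − 0.20) = 40, which reproduces (at 15% loss it would be 42.5). The plan gives no figure for the biopsy interval, and this point does not depend on the sample size.

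**Are the two triggers the same?** The text points both ways.

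1. Section C describes "neoplastic progression of BE to low-grade neoplasia, high-grade neoplasia and finally to esophageal adenocarcinoma". On that usage neoplasia includes low-grade disease, and Group A's trigger is the broader one.
2. Elsewhere Section C says that "imaging modalities to diagnose BE-associated dysplasia or neoplasia have yet to be completely developed", and the inclusion criteria in F1 admit patients under "standard of care endoscopic surveillance for metaplasia, dysplasia, or neoplasia". Here dysplasia and neoplasia are separate terms. On that usage Group A's trigger could be equal to Group B's, or narrower.
3. The same inclusion criterion makes patients who meet only one trigger eligible. Such a patient, in the arm whose trigger is not met, is neither assigned to 1 cm nor clearly under routine surveillance, so the interval is left to judgement.

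**What one affected patient contributes.** Assume four biopsies at every level, with levels at the junction and at each interval above it. Count = 4 × (floor(length ÷ interval) + 1).

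| Segment | 1 cm | 2 cm | Difference |
|---|---|---|---|
| 2 cm | 12 | 8 | 4 |
| 3 cm | 16 | 8 | 8 |
| 4 cm | 20 | 12 | 8 |
| 5 cm | 24 | 12 | 12 |
| 6 cm | 28 | 16 | 12 |

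These are upper-end counts, because islands and tongues of Barrett's mucosa will not always allow four biopsies at a level.

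**What an arm would show.** Mean difference per patient = share meeting only one trigger × difference in the table. The share is not in the documents, so these values are assumed:

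- Share 0: difference 0.
- Share 10%, 2 cm segments: 0.1 × 4 = 0.4.
- Share 30%, 5 or 6 cm segments: 0.3 × 12 = 3.6.
- If only half of these patients receive the other interval: 0.2 to 1.8.

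The sign is fewer biopsies in Group B if Group A's trigger is the broader one, and more in Group B if it is the narrower one.

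**Primary yield.** Take a crude proportion with no HRME effect, a 20% share, 4 cm segments, 3% yield in other patients (12 biopsies each), and Group A's trigger as the broader one.

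- Affected patients with 15% random yield and 2 targeted biopsies at 50%:
  - A = (0.2 × (20 × 0.15 + 2 × 0.5) + 0.8 × 12 × 0.03) ÷ (0.2 × 22 + 9.6) = 7.8%
  - B = (0.2 × (12 × 0.15 + 2 × 0.5) + 0.288) ÷ (0.2 × 14 + 9.6) = 6.8%
- Affected patients with 5% random yield and 4 targeted biopsies at 60%:
  - A = (0.2 × (20 × 0.05 + 4 × 0.6) + 0.288) ÷ (0.2 × 24 + 9.6) = 6.7%
  - B = (0.2 × (12 × 0.05 + 4 × 0.6) + 0.288) ÷ (0.2 × 16 + 9.6) = 6.9%

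In these two cases the shift is one point or less and changes sign with the assumed yields. These are not estimates from the planned GLIMMIX model.

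**The case against.** The strongest reply is that this is loose drafting of a single rule. Both arms use the same two-way split and cite standard of care, and Group B's white-light call is only neoplastic or non-neoplastic, with no separate category for high-grade dysplasia. Section C also says that dysplastic or early cancerous mucosa cannot be told by eye from benign Barrett's mucosa. If suspicion is a white-light judgement, few patients could be placed between the two triggers. This stands as a reason to expect a small effect. It does not remove the conflict: no text says that the rules are one, and neither trigger rules out prior histology as its basis.

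Second, the basis of suspicion is not wholly silent. The Group A text points to the white-light view, and Group B already records a call before imaging. Both are true, but those records concern visible lesions, and neither sets the interval.

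Third, G2 plans no analysis of biopsy count or time, and a larger conflict precedes this one: F1 and the aims describe directed biopsy in Group B, whereas its procedure adds four-quadrant sampling. Resolving that conflict could rewrite the sentence at issue. This limits the weight of the point, which takes the Group B procedure as written.

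A reader might also infer that the wording must lower Group B's count and so favour HRME. The documents do not support that, because it holds on only one of their two usages of neoplasia. Nor do they support the inference that the HRME read decides the interval. Section I bases management on standard endoscopic and pathologic diagnoses, which argues against it, though nothing says so for the interval.

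**Conclusion.** The conflict is real: two triggers for one procedure, with no text to reconcile them. Followed literally, the plan allows patients who meet only one trigger to be biopsied at different density by arm, which bears on aim 1b, on the biopsy part of aim 3 and, probably only slightly, on the primary yield.

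The size cannot be determined. With an assumed share of 0 to 30% and 2 to 6 cm segments, the arms would differ by 0 to 3.6 random biopsies per patient, in either direction. The range rests on full four-quadrant sampling and, at its upper end, on every such patient receiving the other interval. It shows what the gap could do and is not an estimate of bias. The point merits correction because the fix is cheap, not because a large bias has been shown.

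**What to change.** Reconcile the Group A and Group B procedure texts in F2 so that one identical trigger for the closer interval applies in both arms. Which trigger is a matter for the clinical team. State what suspicion rests on, and choose a basis that does not use the HRME read, since Group A has none. Record the resulting interval for every patient, with or without a visible lesion, alongside the white-light diagnosis and plan already required: before HRME imaging in Group B, and at the matching point in Group A.

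The cost is one sentence in the protocol and one field added to records already planned. No extra patients are needed, and the timing of randomisation does not change.

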Section G: Sample Size/Data Analysis

G1. Sample Size

How many subjects (or specimens, or charts) will be used in this study?

Local: 47 Worldwide: 100

Please indicate why you chose the sample size proposed:

Approximately 100 subjects with 50 in the WL-arm and 50 in the HRME-arm. We anticipate that 15-20% of subjects may be not complete their endoscopy for various reasons (lack of biopsies, loss of Barrett's mucosa, visualization of a lesion > 2 cm, inability to complete endoscopy, etc.) which would allow 40 in each arm. Since each patient only requires one visit for enrollment into the study, we expect that 80 patients will be enrolled and randomized and complete the study.

G2. Data Analysis

Provide a description of your plan for data analysis. State the types of comparisons you plan (e.g. comparison of means, comparison of proportions, regressions, analysis of variance). Which is the PRIMARY comparison/analysis? How will the analyses proposed relate to the primary purposes of your study?

In this trial, the randomization will be stratified by risk group: high risk and average risk. All analyses described below will be stratified as well.

The primary outcome of the randomized trial is Diagnostic Yield, defined as the proportion of all biopsies that are truly neoplasia after histopathological review. A generalized linear model for logistic regression with multiple correlated binary outcomes within each patient will be used for data analysis (McCullagh and Nelder, 1989). In this model the binary outcome for each biopsy specimen is whether the specimen is classified as neoplasia or non-neoplasia, and the explanatory variable is the biopsy protocol group (Group A is standard of care, the control group; Group B is the optical biopsy protocol with HRME). PROC GLIMMIX in SAS will be used because of the correlations among samples from the same patient. The model will allow for testing whether the proportion of samples classified as neoplasia differs between the two biopsy protocols. The analysis will be stratified by risk group --- High Risk and Average Risk. A secondary outcome will be the estimation of the accuracy of each biopsy protocol. Because of the small numbers of true neoplasia patients that are expected to be present among patients enrolled in the trial, sensitivity on a patient-basis will not be estimated. However, specificity will be estimated, stratified by risk group, for each of the two biopsy protocols, along with a one-sided 95% confidence interval

Section H: Potential Risks/Discomforts

H1. Potential Risks/Discomforts

Describe and assess any potential risks/discomforts; (physical, psychological, social, legal, or other) and assess the likelihood and seriousness of such risks:

Possible risks associated with the study procedures are listed below. There may also be risks that are not known. Many side effects go away soon after the procedure, but in some cases, side effects may be serious, long-lasting or permanent, and may even cause death. It is important that the participant tell the study staff about any side effects that he/she may have had even if he/she does not think it is related to the procedure.

Proflavine: There is the possibility of a severe allergic reaction (anaphylaxis) to the Proflavine contrast dye in which the participant may have difficulty breathing and their blood pressure may drop. Proflavine may also cause irritation of gastric mucosa resulting in nausea and vomiting. Jaundice and serious toxic hepatitis may also occur. There are procedures in place to treat the participant in the endoscopy room in the event that this happens. Proflavine enhances visualization of the cell nuclei, because of the very low doses used, we have not noted any clinical sequelae or side effects related to the drug.

Specimen Imaging Probe: There are no known risks from the use of the imaging probe.

Anesthesia: There may be additional risks from the added time of additional sedation, such as decreased blood pressure.

Aspiration (inhaling) of fluid into the lungs during endoscopy: This might cause inflammation in the lungs. Safeguards to prevent this from happening while the participant is under anesthesia will be in place during and after the procedure, and participant's breathing and other vital signs will be carefully monitored.

Biopsies: There is the possibility of some hoarseness, sore throat, difficulty and/or pain in swallowing, bleeding or infection, as well as discomfort at the surgical site.

If the participant experiences any symptoms other than those that the study doctor has informed the participant are associated with the procedure, please let the study doctor know.

There always exists the potential for loss of private information; however, there are procedures in place to minimize this risk.

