All patients who fit the study criteria will be consented for HRME with biopsy and possible EMR (similar to colonoscopy with possible polypectomy). Examination of the esophagus, stomach, and small intestine with standard endoscopy will be performed using a high resolution video endoscopy (Olympus). The level of the gastroesophageal (GE) junction will be recorded. The level of the squamo-columnar junction (Z line) will also be recorded. Any proximal displacement of the Z line or gap between the GE junction and Z line will normally raise the suspicion for BE due to the presence of columnar mucosa in the distal esophagus. The maximum length of suspected BE (i.e. distance between the GE junction and Z line) and pattern of the BE (islands, tongues, circumferential columnar epithelium) will be recorded and photographed. A description of the BE using the Prague C&M criteria, which is used to describe the maximal length of BE and extent of circumferential BE, will also be recorded {Sharma, 2006 #4178}. Esophagitis will be described using the Los Angeles classification. The size, morphology, and location in the esophagus of every macroscopically visible lesion will be recorded and described using the 2002 Paris Endoscopic Classification of neoplastic lesions. The height of the mucosal lesion will be assessed by comparison with the diameter of a closed biopsy forceps (2.5 mm) {, 2003 #4280}.

After the endoscopic examination, the endoscopist will provide an endoscopic diagnosis for any visible mucosal lesions (pre-HRME diagnosis: i.e. neoplastic vs. non-neoplastic) and a plan for management during the procedure, such as biopsy or endoscopic mucosal resection (pre-HRME plan). These will be recorded prior to the initiation of HRME imaging.

For the HRME portion of the exam, 5-10 ml of proflavine hemisulfate (0.01%) will be sprayed on the esophageal mucosa. Proflavine is being used under an IND from the FDA (#102217). The HRME itself is an IDE exempt device per the FDA. The HRME will then be inserted through the biopsy channel of the endoscope and gently placed against the mucosa. The endoscopist will image each WL-discrete lesion first from the most distal to the most proximal. For each HRME imaged site, an optical read will be obtained (neoplastic vs. non-neoplastic) followed by a tissue biopsy of the imaged areas.

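### G2 compares yield only between arms and leaves out the HRME read; under the F2 sampling that contrast is expected to be near null, and no within-patient analysis of HRME-selected biopsy is specified

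*SAP*

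**What the plan says.** SAP G2 makes diagnostic yield the primary outcome, "defined as the proportion of all biopsies that are truly neoplasia after histopathological review". In the logistic model, "the explanatory variable is the biopsy protocol group", and the stated purpose is this: "The model will allow for testing whether the proportion of samples classified as neoplasia differs between the two biopsy protocols". Analyses are stratified by risk group. The only other analysis in G2 is the specificity of each biopsy protocol with a one-sided 95% interval; patient-level sensitivity is explicitly not estimated.

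Protocol F2 (Group B procedure) says of discrete lesions: "For each HRME imaged site, an optical read will be obtained (neoplastic vs. non-neoplastic) followed by a tissue biopsy of the imaged areas". It then adds random four-quadrant biopsies of flat mucosa, and says of these: "Prior to the standard tissue biopsy, an HRME read will be obtained from the area (neoplastic vs. non-neoplastic". Each imaged spot is marked for biopsy, and under Pathology each specimen receives its own diagnosis so that it can be matched to the HRME finding.

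Protocol Section D (Aim 1a) and Section F1 describe Group B differently, as HRME followed by directed biopsy. Section D also lists Aim 1b (whether HRME changes biopsy and resection decisions and the number of biopsies) and Aim 2 (sensitivity, specificity, PPV and NPV of HRME against histology).

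**The concern.** Protocol Section C argues that areas read as non-neoplastic may not need biopsy. To test that, one needs the yield at the sites HRME would select, the biopsies it would save and the neoplasia it would leave behind. If Group B is sampled as F2 describes, the data permit all three within the same patients, because both strategies (biopsy every site, or only read-positive sites) can be scored on each patient.

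G2 uses none of this. Its single yield contrast compares different patients. With all Group B biopsies counted, it also compares two nearly identical sampling schemes. The trial could then report no difference in yield while saying nothing about HRME-selected biopsy, and the analysis that does address it would be chosen after the data were seen.

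**Working it through.** **1. The plan's own figure.** SAP G1: "Approximately 100 subjects with 50 in the WL-arm and 50 in the HRME-arm"; "We anticipate that 15-20% of subjects may be not complete their endoscopy"; "which would allow 40 in each arm". 50 × (1 − 0.20) = 40 per arm, 80 in total, so the figure reproduces at 20% loss (15% gives 42.5). This is attrition arithmetic only. No effect size, alpha, power, neoplasia rate, intra-patient correlation (ICC) or number of biopsies per patient is stated.

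**2. What the arm contrast estimates under each reading.**

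| Group B sampling and counting | G2's contrast | Within-patient analysis |
|---|---|---|
| Aim 1a / F1: directed sites only | HRME-directed yield against full sampling | Not possible: no histology at read-negative sites |
| F2, all biopsies counted (G2's definition as written) | Full sampling against full sampling; expected odds ratio near 1 | Possible |
| F2, only read-positive biopsies counted (a rule G2 does not state) | PPV in B against full-sampling yield in A | Possible |

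The second row is near 1 rather than exactly 1. The triggers for 1 cm spacing are worded differently in the two arms (suspected neoplasia in A, suspected high-grade dysplasia in B), and imaging may shift where in a quadrant the forceps goes.

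**3. Pilot inputs (Protocol Section C).** Sensitivity 0.81, specificity 0.85, NPV 0.95. Solving 0.95 = 0.85(1 − p) / [0.85(1 − p) + 0.19p] gives p = 0.0425 / 0.223 = 0.19. Then D = 0.81 × 0.19 + 0.15 × 0.81 = 0.275, and PPV = 0.154 / 0.275 = 56%.

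**4. What the within-patient analysis would show.** Assume 40 patients with 12 sites each (480 sites) and the pilot accuracy. The share of read-positive sites is D = 0.81p + 0.15(1 − p).

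| Assumed site rate p | Yield, all sites | Yield, read-positive sites (PPV) | Read-positive / avoided | Neoplastic sites skipped |
|---|---|---|---|---|
| 0.03 | 3% | 0.0243/0.1698 = 14% | 82 / 398 | 0.19 × 14.4 = 3 of 14 |
| 0.10 | 10% | 0.081/0.216 = 37.5% | 104 / 376 | 0.19 × 48 = 9 of 48 |
| 0.19 | 19% | 0.1539/0.2754 = 56% | 132 / 348 | 0.19 × 91.2 = 17 of 91 |

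**5. Why pairing helps, and why the scale matters.** With constant read accuracy, logit(PPV) − logit(p) = log(0.81/0.15) = log 5.4 = 1.69 for every p. On the log-odds scale, chance variation in Group B's neoplasia rate therefore cancels. On the risk-difference scale it does not: the slope of PPV − p with respect to p is 0.81 × 0.15 / D² − 1, which is 0.60 at p = 0.19 and 3.21 at p = 0.03.

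**6. Simulated variance ratios.** These compare read-positive yield in B against all sites in A with read-positive yield in B against all sites in the same B patients, at 40 patients per arm.
- Log-ratio scale, logit-normal patient effects (SD 1.5 to 2.5, site rate 7 to 17%): SD 0.29 to 0.55 between arms and 0.11 to 0.14 within patients, a variance ratio of 5.6 to 15.2. Two further simulations of this kind gave 5 to 17 and 5 to 13.
- Same scale, beta-binomial model, ICC 0.1 to 0.5, read accuracy varying between patients: 3.0 to 24.
- Log-odds scale, beta-binomial: 2.7 to 51 for ICC 0.1 to 0.5; 1.7 to 5.9 at ICC 0.
- Risk-difference scale, beta-binomial, all settings: 1.4 to 5.0 (ratio of standard errors 1.2 to 2.2).

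One setting on two scales (19%, 8 biopsies, ICC 0.3, constant accuracy): log-odds SE 0.39 against 0.16, variance ratio 5.8; risk-difference SE 0.083 against 0.047, variance ratio 3.2.

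**The case against.** The strongest reply is that the trial already plans this. Yield at read-positive sites is the PPV, and the fraction of neoplastic sites skipped is one minus sensitivity; both belong to Aim 2. Biopsy counts belong to Aim 1b. The proposed contrast rearranges the same two-by-two table. This largely stands, and it narrows the point: the objectives do not ignore the read, but G2 gives Aims 1b and 2 no method, no handling of clustering and no contrast with full sampling.

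A reader might go further in four ways that the documents do not support.
- That the analysis needs no precondition. It is possible only if read-negative sites are biopsied; F2 says so, while Aim 1a and F1 say directed biopsy.
- That the within-patient contrast is several times more precise as a matter of fact. The documents give no ICC, neoplasia rate or biopsy count, and on the risk-difference scale the gain can be as small as 1.4 in variance.
- That it has far more power for the same question. PPV exceeds the overall yield exactly when sensitivity exceeds 1 − specificity, so the paired test rejects only an uninformative read. The randomised contrast compares protocols as performed, so setting the two powers side by side is not like for like.
- That it should replace the randomised comparison. It is not randomised. Reads also follow a white-light diagnosis and are made knowing that a biopsy comes regardless, so thresholds may differ from practice in which a negative read means no biopsy.

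**Conclusion.** The point holds as a gap in G2, conditional on how Group B is sampled. If F2 governs and all biopsies count, the planned yield contrast is expected to be near null and does not estimate HRME-selected yield; the within-patient Group B contrast does. On pilot accuracy it would be about 56% against 19% (ratio 2.9), with about one neoplastic site in five (19%) skipped. If Aim 1a and F1 govern, the within-patient analysis cannot be done, and neither can the sensitivity, specificity and NPV of Aim 2.

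The direction of the precision gain was the same in every setting tried. Its size depends on assumed clustering and neoplasia rate: roughly 5 to 15 times less variance on the log-ratio scale in most clustered settings (wider under the beta-binomial model), and 1.4 to 5 times on the risk-difference scale. The case for the analysis rests mainly on what it estimates and only secondarily on precision.

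**What to change.** 1. Reconcile Aim 1a and F1 (directed biopsy) with the Group B procedure in F2 (random four-quadrant biopsies, each with a read). State in G2 which Group B specimens enter the primary yield.
2. If read-negative sites are biopsied, add a secondary analysis to G2, in Group B only, as the method for Aims 1b and 2. Compare the yield among read-positive sites (PPV) with the yield among all sites in the same patients, overall and by risk group. Name the scale in advance. Take the 95% interval from a patient-level bootstrap or a cluster-robust variance, since read-positive sites are a subset of all sites and biopsies cluster within patients.
3. Report with it the number of biopsies avoided and the numbers of neoplastic sites and of patients with neoplasia that would have been missed. Without these, the contrast shows only that the read is informative. Where a risk group has very few neoplastic sites, give counts rather than a ratio.
4. State that the analysis is not randomised, that reads were made knowing a biopsy would follow, and that it supplements the randomised comparison.

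The cost is the reconciliation, one paragraph in G2 and one further analysis of data that F2 already collects. No patient undergoes any additional procedure.
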